User-driven Retrospectively Supervised Classification Updating (RESCU) System for Robust Upper Limb Prosthesis Control

NCT04043234

December 29, 2023

This study will compare the use of RESCU [Experimental] Prosthesis with a [Standard] pattern recognition prosthesis in a clinical setting and in unsupervised daily activity. The protocol will follow a single case experimental design (SCED) to compensate for the limited size of the patient population. Each of the participants will use the Standard and Experimental systems over a 35-day period. The Standard system will include a multi-articulated hand, eight EMG electrodes, and a commercially-available pattern recognition controller. The *RESCU* system will also use the multi-articulated hand, similar to the Standard system, but will differ with respect to incorporating eight *IBT Element Electrodes* (as required for pattern recognition control) and the *RESCU* control software.

**Participants:** We will recruit a total of 10 unilateral trans-radial amputees based on the inclusion and exclusion criteria noted in the Clinical Protocol. Note: the *RESCU* system is applicable to a range of amputation levels, but this study is focused on trans-radial amputees as they represent the largest population of users.

**Procedures:** After informed consent and medical clearance are completed, participants will be fitted by the study prosthetist.

On **Day 0**, the participant will be evaluated with the Standard prosthesis. A series of **Measures** (as defined in the next paragraph) will then be recorded. The participant will then take the prosthesis home for 1 week, and daily use data will be recorded. The participant will return to the clinic for **Day 7 Measures** and download of the daily use data. During this same session, the participant will be fit with the second system, instructed on the controller's use, and **Measures** will be recorded. There will be no washout period as the prosthesis is expected to be in daily use. The participants will go home for a four-week period and return on **Day 35** for a second set of **Measures**. At this time, the participant will be asked which prosthesis he/she prefers, and this will be the prosthesis that they return home with at the end of the study.

There are limited functional outcome assessment options for the planned comparison. However, we will test functional measures at the clinic appointments, examine daily use data, and administer several qualitative surveys to assess participant outcomes.

**Measures (each appointment day):** **First**, a validated measure of upper extremity impairment will be used: the Activities Measure for Upper Limb Amputees (AM-ULA). The AM-ULA is a clinician-graded measure of activity performance for adults with upper limb amputation that considers task completion, speed, movement quality, skillfulness of prosthetic use, and independence to quantify how functional an individual is while using their prosthesis. A higher score indicates overall greater prosthesis functionality. This test has been validated for normative data.

**Second**, we will ask participants to record daily use data with the Standard and Experimental systems:

**Mean Daily Prosthesis Use Duration:** Our hypothesis is that *RESCU* will improve prosthesis acceptance. In addition to the subjective measures used below, we will measure the mean duration of daily prosthesis use as a proxy for improved prosthesis acceptance. We will compare the mean daily use for the Standard and Experimental systems, hypothesizing that the Experimental system will be used more than the Standard system. **This will be our primary outcome measure.**

**Third**, we will use a suite of validated survey instruments directly related to prosthesis use and satisfaction. These instruments are the Orthotics and Prosthetics User Survey Upper Extremity Functional Status (OPUS-UEFS) [53], the Trinity Amputation Prosthesis Experience Scale (TAPES), and various Patient Reported Outcomes Measurement Information System (PROMIS) subscales (e.g., Pain Interference, Satisfaction Short Form 8a). In addition, we will report the percentage of participants that preferred the *RESCU* system.

**Statistics:** Our primary outcome measure will be the mean daily prosthesis use duration. We hypothesize that the mean daily use for those using the Standard system will be increased from 4.0 to 6.0 hours. In order to detect such a difference, using a paired t-test calculating the mean difference between the use of the two systems, and assuming no period effect and no carryover effect, 10 pairs of measurements would be needed. A two-sided t-test achieves 80% power to infer that the mean difference is not 0.00 when the total sample size of a 2x2 crossover design is 20 (10 patients), the actual mean difference is 2.00, the standard deviation of the paired differences is 3.00, and the significance level is 0.050.

**Data analysis:** Data will be gathered and evaluated carefully by study team members without conflicts of interest to determine the distribution of all scores in the population studied and the variability of scores within and between uses of the two systems. We will specifically examine whether daily use improves by week of use. Personal

characteristics will be used to stratify analyses as applicable. As stated above, we will compare the mean daily use duration of the two systems using a paired t-test, and attempt to determine if there is a period effect, i.e., trend over time. We will also test to assure that there is no sequence effect. We anticipate that the system preferred by the participant will also demonstrate an increased mean daily use duration.

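### The plan claims a single case design to offset the small population, but one switch on a common day and a group paired t-test cannot supply that, and device stays confounded with study day

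*Combined protocol and SAP*

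**What the plan says.** The opening overview of the combined protocol and SAP states: "The protocol will follow a single case experimental design (SCED) to compensate for the limited size of the patient population". Under Participants: "We will recruit a total of 10 unilateral trans-radial amputees".

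Procedures then gives one schedule for everyone.
- On Day 0, "the participant will be evaluated with the Standard prosthesis".
- "The participant will then take the prosthesis home for 1 week, and daily use data will be recorded".
- At the Day 7 visit: "During this same session, the participant will be fit with the second system".
- "The participants will go home for a four-week period and return on Day 35 for a second set of Measures".
- "There will be no washout period as the prosthesis is expected to be in daily use".

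No return to the first system is described, and no staggered or random switch day.

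Under Data analysis, the primary comparison is: "we will compare the mean daily use duration of the two systems using a paired t-test". The same paragraph adds a look at use by week, at variability within and between uses of the systems, and at a possible period effect, with no method for any of them. Statistics calls the design a 2x2 crossover and sizes it on the assumption that period and carryover effects are absent. Data analysis also plans a test for a sequence effect, although Procedures describes only one sequence.

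**The concern.** A single case design makes up for few participants by drawing inference from many repeated measurements within each person. To separate the intervention from the passage of time, the phase change must be repeated within the person or fall at different times, ideally random ones, in different people. Here it happens once per person and on the same study day for all. The primary test then reduces about 35 daily values per person to one difference.

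Two things are at stake. The report could claim single case rigour for what is, on the Procedures text, a before-after comparison in 10 people. And a shared change in use over the five weeks cannot be told apart from a device effect. The plan itself regards such a change as possible, since it intends to look at use by week.

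**Working it through.** **1. The plan's own power figure.** Inputs from Statistics: mean difference 2.00 h, SD of paired differences 3.00 h, two-sided alpha 0.05, 10 patients, stated power 80%. For a paired t-test the noncentrality is difference/(SD/√n), with n − 1 degrees of freedom.
- n = 10: 2/(3/√10) = 2.11; power 46.9%.
- n = 20: 2/(3/√20) = 2.98; power 80.7%.

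The stated 80% fits 20 patients, not 10. That is a separate matter. It is relevant here only because the gain from self-pairing is already inside the SD of paired differences, so pairing is not an extra benefit that the single case label could refer to.

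**2. Can device be separated from study day?** Let D = 1 on the second system and 0 on Standard, for 10 participants over 35 days. After participant and day effects are removed, what remains is D − (participant mean) − (day mean) + (overall mean). With a common Day 7 switch, D equals its day mean for every participant, and each participant mean equals the overall mean, 28/35 = 0.8. Every residual is 0, so the residual sum of squares is 0. Without an assumption about the shape of the trend, the daily data carry no information that distinguishes device from day.

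**3. Size of the consequence.** Suppose there is no device effect but mean use shifts by a common amount between the first 7 and the last 28 days. The paired t-test treats the shift as the difference. With the formula in step 1, SD 3.00 and n = 10:

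| Assumed common shift | Chance of a significant result |
|---|---|
| 0.5 h | 7.6% |
| 1.0 h | 15.7% |
| 2.0 h | 46.9% |

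The nominal rate is 5%. The last row equals the power in step 1 because it is the same calculation. The documents give no trend, so the shifts are assumptions. For scale, the midpoints of days 1–7 and 8–35 are 4 and 21.5, which is 17.5 days apart. A steady drift giving a 1.0 h shift is 60/17.5 = 3.4 minutes per day.

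**4. What a staggered switch would and would not buy.** Illustrative switch days, evenly spread: 7, 7, 8, 9, 10, 11, 12, 13, 14, 14. The residual sum of squares from step 2 becomes 12.8, so the device effect is estimable. If the device effect were the same in everyone and days were independent, the standard error would be σ/√12.8 = 0.28σ, where σ is the day-to-day SD. For assumed σ of 2 or 3 h that is 0.56 or 0.84 h.

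Those figures do not fit the plan's own SD. Over 7 and 28 independent days, day noise contributes σ²(1/7 + 1/28) to a paired variance of 3.00² = 9:
- σ = 2: 0.71, leaving τ² = 8.29 (SD 2.88 h) between participants.
- σ = 3: 1.61, leaving τ² = 7.39 (SD 2.72 h).

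Allowing for this, SE² = σ²/12.8 + τ²Σw², where w is each participant's share of the 12.8. For this schedule Σw² = 0.117.
- σ = 2: √(0.3125 + 0.969) = 1.13 h.
- σ = 3: √(0.703 + 0.864) = 1.25 h.

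The paired t-test has 3/√10 = 0.95 h. Truly random switch days over Days 7–14 do a little worse than this even spread: the multiplier of σ has a median of 0.31 instead of 0.28.

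**The case against.** Several points on the other side are sound.

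- **The A-B sequence is repeated in 10 people.** True, but at the same study time in each, so the repetition does not separate device from day.
- **The daily data are used.** A reader might infer that they are collected and thrown away. That goes too far, because Data analysis looks at use by week, variability and trend. These looks have no stated method, and the primary test does not use the daily series.
- **The sample size does not rest on the single case sentence.** A reader might take that sentence as the reason why 10 is enough. The number comes from the power calculation under Statistics, which never invokes a single case design. The sentence justifies the type of design.
- **The crossover wording.** If order did vary, say 5 and 5, the residual would be −0.8 on 7 days and 0.2 on 28 for one order, with signs reversed for the other. The residual sum of squares would be 10 × (7 × 0.64 + 28 × 0.04) = 56, and device would be estimable. But Procedures describes Standard first only, and a crossover with one Day 7 switch each would still be a group crossover, not a single case design.
- **A randomisation test.** With only one possible switch day, such a test could never give a p-value below 1. The plan proposes no such test, so this shows no error in a planned analysis.
- **Staggering is no full cure.** Fitting, instruction and measurement take place at the switch visit, so they move with it. It would be wrong to expect staggering to remove the effect of that contact, or to sharpen the estimate.

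**Conclusion.** The concern holds in a limited form. The plan claims a design property that neither its schedule nor its primary analysis has, and under the single order in Procedures any effect tied to study day falls wholly into the device comparison. For common shifts of 0.5 to 2.0 h, the false-positive rate of the primary test would be about 8% to 47%. This assumes the plan's SD of 3.00 h, 10 complete pairs and no device effect; the shifts are illustrative.

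The documents do not show that such a trend exists or how large it would be. Nor do they support the inference that a true single case design would have made 10 participants as informative as more. On the plan's own SD, and with assumed daily SDs of 2 to 3 h and independent days, adjusting for study day would cost precision.

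**What to change.** **Preferred, wording only.** Delete the single case sentence and its compensation rationale. Describe the trial as an uncontrolled before-after comparison and limit the conclusion to that. Reconcile the one-order schedule in Procedures with the 2x2 crossover and the sequence-effect test under Statistics and Data analysis. This costs nothing in conduct.

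**Alternative, if the sponsor wants to keep the claim.** Randomise each participant's switch visit over a short window chosen by the sponsor. Prespecify either a randomisation test on the switch day or a mixed model of daily use with participant, day and device effects. The model must let the device effect vary between participants; without that it would overstate precision.

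This needs no extra visits or participants, and the daily data are already planned. Its costs and limits are:
- a standard error of about 1.1 to 1.25 h in place of 0.95 h, on the assumptions above;
- a shorter second phase: if the window ran to Day 14, up to 7 of 28 days, a quarter, would be lost;
- refit, instruction, attention and novelty at the switch visit stay confounded with the device, and the report should say so.

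### Does changing the electrodes together with the control software undermine the comparison of the RESCU and Standard systems?

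*Combined protocol and SAP*

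**What the plan says.** The overview states the aim as comparing the RESCU prosthesis "with a [Standard] pattern recognition prosthesis in a clinical setting and in unsupervised daily activity". It then lists the parts of each system. For the comparator: "The Standard system will include a multi-articulated hand, eight EMG electrodes, and a commercially-available pattern recognition controller". The RESCU system uses the multi-articulated hand and is described as "similar to the Standard system, but will differ with respect to incorporating eight" IBT Element Electrodes, plus the RESCU control software. The only remark on the choice of electrodes is the parenthesis "as required for pattern recognition control".

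Under Mean Daily Prosthesis Use Duration, the hypothesis appears in two forms. The general one is that RESCU "will improve prosthesis acceptance". The operational one, attached to the primary outcome, is "hypothesizing that the Experimental system will be used more than the Standard system".

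Classification updating is mentioned once, in the document title: "User-driven Retrospectively Supervised Classification Updating (RESCU) System for Robust Upper Limb Prosthesis Control".

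**The concern.** The name RESCU stands for a way of updating a classifier, so a reader expects the trial to show whether that updating makes people wear the prosthesis longer. For that question the two systems should differ in the software only. They also differ in the electrodes, which supply the signal to any pattern recognition controller. Each participant changes both components together at the Day 7 visit. A longer daily use could then come from the software, from the electrodes, or from both.

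The stated reason for the electrodes does not remove the worry. The Standard system is also a pattern recognition system with eight electrodes, so that requirement is met on both sides and does not explain a different type.

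At stake is the interpretation of a positive result: it could be reported as evidence for user-driven updating when it supports only a statement about the complete device.

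**Working it through.** The document gives no figure for the electrode or software contribution, so there is none to reproduce. The check is what the design identifies, set against what the plan claims.

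**1. What differs.** From the overview:

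| Component | Standard | Experimental |
|---|---|---|
| Hand | multi-articulated | multi-articulated |
| Number of electrodes | 8 | 8 |
| Electrode type | EMG electrodes, make not stated | IBT Element Electrodes |
| Control | commercial pattern recognition controller | RESCU software |

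Two rows differ, and the text itself presents both as differences.

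**2. What can be estimated.** Let E be the effect of the electrodes on mean daily use, S the effect of the software, and I any interaction. Setting period effects aside, the mean paired difference estimates

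D = E + S + I.

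No period pairs one electrode type with both controllers, so there is one equation and up to three unknowns. The Statistics section plans for daily use that "will be increased from 4.0 to 6.0 hours", so D = 6.0 − 4.0 = 2.0 hours. With I = 0, the following fit equally well:

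- S = 2.0, E = 0
- S = 1.0, E = 1.0
- S = 0, E = 2.0
- S = 2.5, E = −0.5

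The last line shows that the software share need not lie between 0% and 100%, because the two effects may have opposite signs. The paired t-test, the period and sequence checks and the stratified analyses named under Data analysis cannot separate E from S. The aliasing is real.

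**3. What the plan claims.**

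- Aim (overview): prosthesis against prosthesis.
- Operational hypothesis (primary outcome): Experimental system against Standard system.
- Planned effect (Statistics): the total, D = 2.0 hours.
- Preference endpoint (end of Measures): percentage preferring the RESCU system.
- Title: classification updating, as the expansion of an acronym attached to the word System.

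The first four concern D. None states a value, test or conclusion for S. The remaining hypothesis sentence uses RESCU without the word system, but the next sentences make it operational as a system comparison.

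**4. What the possible changes would do.**

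- *Same electrodes in both systems.* The target moves from D to S for the chosen electrode. If the IBT electrodes go into both, the comparator is no longer the Standard system with its own electrodes. If the Standard electrodes go into both, the Experimental device is no longer the RESCU system as defined. The document does not say whether either controller accepts the other's electrodes.
- *Rewording the hypothesis to system against system.* The operational hypothesis already has this form and the overview already lists the components. D, its test and the number of participants are unchanged.

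**The case for a change.** The strongest case for acting is that the plan uses one word for three things: the method in the title, the control software in the overview, and the whole device elsewhere. It never says outright which of these the trial evaluates. A sponsor with a positive result could slide from the device to the algorithm, and one added sentence would prevent that at no cost.

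Part of this stands. The usage is loose, and a conclusion about updating alone would be unsupported. But the plan does not commit itself to that conclusion, and where it becomes operational it names the two systems. A caveat against a claim the plan does not make belongs in the report and does not amend the design or analysis.

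It is also fair to ask whether even the whole-system attribution is secure. Under Procedures the Standard system is used first and the second system from Day 7 to Day 35, so system and period change together. That is a separate matter, which common electrodes would not resolve.

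**Conclusion.** No change to the plan follows. Electrodes and software are completely aliased, and the software's share of any difference cannot be estimated. However, the comparison the plan sets out is between complete systems, the electrodes are part of the Experimental system by definition, and the primary hypothesis remains valid as a question. The effect on the planned estimate, test and sample size is nil.

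This rests on reading the hypothesis as the plan makes it operational, Experimental system against Standard system. If the intended claim were about classification updating by itself, the design could not support it at any sample size. Evaluating a complete new device against a complete commercial one is a fair choice of question, and isolating the software is a different study. An analyst reporting this trial would sensibly use the term RESCU system throughout and note that the effect of the updating software alone was not estimated. The size of the hardware difference is unknown, because the make of the Standard electrodes is not given.

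### The stated 80% power does not follow from the plan's own inputs: 10 patients give about 47%, and 80% needs 20 patients

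*Combined protocol and SAP*

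**What the plan says.** The Statistics paragraph names the outcome: "Our primary outcome measure will be the mean daily prosthesis use duration". It hypothesises a rise from 4.0 to 6.0 hours, tested with a paired t-test, and concludes: "assuming no period effect and no carryover effect, 10 pairs of measurements would be needed". The power claim comes next: "A two-sided t-test achieves 80% power to infer that the mean difference is not 0.00". The sample size and effect attached to that claim read: "when the total sample size of a 2x2 crossover design is 20 (10 patients), the actual mean difference is 2.00". The variability and error rate complete the list of inputs: "the standard deviation of the paired differences is 3.00, and the significance level is 0.050".

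The Data analysis paragraph confirms the test: "we will compare the mean daily use duration of the two systems using a paired t-test". The Participants paragraph confirms the number: "We will recruit a total of 10 unilateral trans-radial amputees".

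**The concern.** The power statement gives two sample sizes at once, 20 and 10 patients. The SD is defined as that of the paired differences, so the pairing is already in the SD and each patient counts once. Two measurements on each of 10 patients are 10 observations for this test, not 20. A standardised difference of 2.00/3.00 = 0.67 is too small for 10 pairs to give 80% power with a two-sided t-test.

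This is the only sample-size calculation given for the primary outcome. If the power is overstated, a non-significant result could be read as evidence against a benefit when the trial had less than an even chance of detecting the hypothesised effect.

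**Working it through.** **Inputs.** All but the last come from the Statistics paragraph; the last is also in the Participants paragraph.

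- Mean difference d = 6.0 - 4.0 = 2.00 h
- SD of the paired differences s = 3.00 h
- Two-sided significance level 0.05, t-test
- Stated power 80%
- Patients n = 10, each giving one Standard-Experimental difference

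**Formula.** For a paired t-test, the noncentrality parameter is ncp = d / (s/√n) = (2/3)√n, with n - 1 degrees of freedom (df). Power is the probability that a noncentral t variable with this ncp falls outside ± the 5% two-sided critical value.

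**The plan's figure at 10 patients.** ncp = (2/3)√10 = 2.108; the critical value with 9 df is 2.262. Power = 46.9%. With the 8 df of a two-sequence crossover analysis it is 45.8%. The stated 80% is not reproduced; the gap is 80 - 46.9 = 33.1 percentage points.

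**Where 80% is reached.**

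| Patients | ncp | Power, df = n - 1 | Power, df = n - 2 |
|---|---|---|---|
| 8 | 1.886 | 37.1% | 35.5% |
| 9 | 2.000 | 42.1% | 40.8% |
| 10 | 2.108 | 46.9% | 45.8% |
| 19 | 2.906 | 78.5% | 78.2% |
| 20 | 2.981 | 80.7% | 80.5% |

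The stated 80% matches 20 patients.

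**Other readings at 10 patients.**

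- One-sided 0.05: 61.9%. The plan says two-sided.
- Normal approximation, two-sided: 55.9%. The plan says t-test.
- 3.00 taken as the within-patient SD, so that the SD of differences is 3√2 = 4.24: 26.6%.
- SD of differences taken as 3/√2: 75.6% with 9 df, 74.3% with 8 df. It gives 80.5% only with 18 df, which 10 differences cannot supply. Its ncp is 2√10/(3/√2) = (2/3)√20 = 2.981, so this is the 20-patient calculation under another name.

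**What 10 patients would need for 80% power (9 df).** Either a true difference of 2.99 h with SD 3.0 h, or an SD of 2.01 h with a difference of 2.0 h. Power for 2.0 h by SD:

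| SD of differences | Power at n = 10 |
|---|---|
| 2.0 h | 80.3% |
| 2.5 h | 61.6% |
| 3.0 h | 46.9% |
| 3.5 h | 36.5% |

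Power falls below 50% once the SD exceeds 2.88 h.

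**What a result would look like.** With n = 10 and an observed SD of 3.0 h, the 95% CI half-width is 2.262 × 3/√10 = 2.146 h. An observed difference of exactly 2.0 h gives t = 2.0/(3/√10) = 2.11, p = 0.064, and a CI of 2.0 ± 2.146 = -0.15 to 4.15 h.

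Under the planned values (true difference 2.0 h, SD 3.0 h), a simulation of 400,000 trials gave 53.1% non-significant results. In 50.7% of all trials the result was non-significant and the CI still contained 2.0 h; in 2.4% it was non-significant and the CI excluded 2.0 h.

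**The case against.** The strongest objection is that the inputs contradict the stated power without showing which number is wrong. An SD of 2.0 h with 10 patients would also give 80%, so 3.00 could be the slip, and the source of the SD may lie in the separate Clinical Protocol, which is not among the documents. This stands in part. The documents reviewed give no source for the SD, and the sponsor should check the original calculation before rewriting. It does not rescue the sentence, which states every input and a power those inputs do not give.

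A second objection is that the population is small: the opening paragraph says the design was chosen for that reason. That may justify enrolling 10 patients. It does not make the power 80%, and the plan itself rests the number on a group-level paired t-test.

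A third is that the Procedures paragraph describes Standard first and then the second system, not a two-sequence crossover, so the df for a 2x2 crossover do not fit. That is fair, and 9 df is the natural choice for the planned test. The two versions differ by about one percentage point, and the conclusion is the same.

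The cause cannot be settled from the text. A total of 20 subjects may have been read as 20 measurements, or 10 per sequence may have been copied as 10 in total. The finding does not depend on which.

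**Conclusion.** The power statement is wrong as written. With a mean difference of 2.0 h, an SD of the paired differences of 3.0 h and a two-sided 0.05 paired t-test, 10 patients give 46.9% power, and 80% is first reached with 20. No reading consistent with the text gives 80% with 10 patients.

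The figure of 47% rests on the stated SD, on the plan's assumption of no period or carryover effect, and on all 10 patients providing data under both systems. The documents reviewed state no dropout allowance (the separate Clinical Protocol may). One or two losses would reduce power to 42% or 37%.

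The error concerns the primary outcome and should be corrected. It affects the justification of the sample size and the reading of a non-significant result; it does not invalidate the planned test.

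**What to change.** 1. Retrieve the original calculation and confirm that 3.00 h is the intended SD of the paired differences. If another value was used, state it with its source and give the power that follows from it.
2. If 3.0 h stands, drop the claim that 10 pairs suffice for 80% power and replace the power sentence with, for example:

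> With 10 patients (10 paired differences), and taking period and carryover effects to be absent, a two-sided 0.05 paired t-test has about 47% power to detect a mean difference of 2.0 h if the SD of the paired differences is 3.0 h. The difference detectable with 80% power is about 3.0 h.

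3. Report the primary result with its 95% CI (half-width about 2.1 h if the SD is 3.0 h), and judge a non-significant result by whether the interval still contains the hypothesised 2.0 h. At an observed SD of 3.0 h, a mean between -0.15 and +2.15 h leaves both 0 and 2.0 h in the interval. A non-significant mean below -0.15 h excludes 2.0 h; for example, -0.5 h gives -2.65 to 1.65 h.

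The cost is a change of protocol wording, including one sentence on reporting. No extra patients, visits or procedures are needed. The downside is a less favourable stated power, which may prompt questions about the sample size.

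### With only one device order described, a trend over time cannot test for the period effect that the sample size assumes away

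*Combined protocol and SAP*

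**What the plan says.** All references are to the combined protocol and SAP.

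- **Statistics.** "Our primary outcome measure will be the mean daily prosthesis use duration". The hypothesis is that use "will be increased from 4.0 to 6.0 hours". The calculation takes it that "the actual mean difference is 2.00" and "the standard deviation of the paired differences is 3.00", for a two-sided paired t-test at the 0.05 level, "assuming no period effect and no carryover effect". The design is called a 2x2 crossover.
- **Data analysis.** Alongside the paired t-test, the team will "attempt to determine if there is a period effect, i.e., trend over time". A test for a sequence effect is also planned. A separate sentence, earlier in the paragraph, reads "We will specifically examine whether daily use improves by week of use". No model, contrast, set of weeks or decision rule is given for any of these.
- **Procedures.** The participant starts on the Standard system on Day 0. "The participant will then take the prosthesis home for 1 week, and daily use data will be recorded". The second system is fitted at the Day 7 visit without washout and used for four weeks, to Day 35. No other starting order is described.

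**The concern.** The Data analysis sentence defines a period effect as a trend. The two are different: use can jump at Day 7 and then stay flat (refitting, new instruction, novelty), which is a period effect without a trend. Use can also rise week by week on one device through learning, which is a trend that says little about the contrast between periods.

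Under a single order the problem goes beyond terminology. Every participant changes period and device at the same visit, so any level shift at Day 7 enters the paired difference in full and is credited to the device. The absence of that shift is an assumption of the primary analysis. The plan offers a check of it that this design cannot perform, and a reported finding of no period effect would be reassurance without content.

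**Working it through.** **Inputs.** From Statistics: means 4.0 h and 6.0 h, difference 2.00 h, SD of paired differences 3.00 h, two-sided alpha 0.05, 10 patients. From Procedures: Standard in week 1, second system in weeks 2 to 5. The documents give no weekly variance, drift or size of period shift.

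**1. The plan's own figure.** The noncentrality is 2.00 / (3.00/√10) = 2.108 with 9 df, and the exact power is 46.9%, not the stated 80%. With 20 patients it is 80.7%. That discrepancy is a separate matter; this point does not depend on it.

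**2. Can period and device be separated?** Write each period's mean use as intercept + period + device.

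| Order | Period | Intercept | Period column | Device column |
|---|---|---|---|---|
| Standard first | 1 | 1 | 0 | 0 |
| Standard first | 2 | 1 | 1 | 1 |
| Second order, if used | 1 | 1 | 0 | 1 |
| Second order, if used | 2 | 1 | 1 | 0 |

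With the first two rows only, the period and device columns are identical: rank 2 for 3 parameters. With all four rows the rank is 3. Under one order only the sum, device plus period, can be estimated.

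**3. Slope within the four-week system.** A pure shift of 2 h at Day 7 gives 6, 6, 6, 6 in weeks 2 to 5. With centred weeks −1.5, −0.5, 0.5, 1.5 (sum of squares 5), the slope is (−9 − 3 + 3 + 9)/5 = 0. This holds for a shift of any size, so a 5% test finds nothing about 95% of the time. Standard has one week and so has no weekly slope to compare.

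**4. Slope over weeks 1 to 5.** The profile is 4, 6, 6, 6, 6, the same whether the step comes from the device or the period. With centred weeks −2 to 2 (sum of squares 10), the slope is (−8 − 6 + 0 + 6 + 12)/10 = +0.40 h/week. The hypothesised device effect appears as a trend although none exists.

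**5. What the paired t-test does meanwhile.** With no device effect and a 2 h period shift, the calculation is that of step 1: it rejects in 46.9% of trials, against a nominal 5%. For a 1 h shift the figure is 15.7%.

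**6. A true linear drift.** The mean of weeks 2 to 5 lies at week 3.5, which is 2.5 weeks after week 1. A drift of 0.8 h/week with no device effect therefore yields 0.8 × 2.5 = 2.0 h, the whole target. A drift of 0.5 h/week yields 1.25 h, about 63% of it.

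**7. Illustrative detection rates.** Suppose independent weekly noise makes up 100%, 50% or 25% of the variance of the paired difference. At 100%, s√(1 + 1/4) = 3.0 gives s = 2.68 h, and the SD of one participant's four-week slope is 2.68/√5 = 1.20.

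| Share of variance that is weekly noise | Power of four-week slope for 0.5 h/week drift | Pure 2 h device step flagged as a five-week trend |
|---|---|---|
| 100% | 21.9% | 26.6% |
| 50% | 38.4% | 33.7% |
| 25% | 65.1% | 39.2% |

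These rates also assume the same drift in every participant. Under other noise assumptions (weekly SD 0 to 2 h) the last column ran from 33% to 47%.

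**The case against.** **The plan never makes the week-of-use look its period test.** This is correct. The two sentences are separate, and a reader might infer from their closeness that one is the method for the other. The documents do not say so. The week-of-use analysis is a reasonable description of learning or habituation and should stay.

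**No method is specified, so the two fits above are the reviewer's.** This is also correct. A model with both a device step and a time trend fits the text and would not mistake the device step for a slope. It still does not test for a period effect: with intercept, device, trend and a Day 7 period step, the weekly design has rank 3 of 4. A day-level version with a slope for each system shares the fault. Its device step is 2.0 h for a pure 2 h device effect and for a pure 2 h period effect. Under a drift of 0.5 h/week with no device effect it is 0.5 h, one week's drift.

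**The crossover label and sequence test imply two orders.** If two balanced orders were used, the +0.40 and −0.40 h/week slopes would average to zero and period could be estimated. But the Procedures describe Standard first and no other order, so there is no second sequence to compare. The contradiction is itself something to resolve.

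**The check is exploratory and has no decision rule.** This stands. A reader might infer that a flat trend will be taken to validate the t-test, or a trend to overturn it; the plan states neither. What remains is that it promises to look for a period effect by a route that cannot show one.

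**Conclusion.** The point holds, and the plan should be amended. Given the single order in the Procedures, no trend result, flat or otherwise, bears on whether there was a shift between periods, and the paired difference estimates device plus period. The slopes of 0 and +0.40 h/week are arithmetic and need no variance assumption. The 46.9% uses the plan's SD of 3.00 h with 10 participants and supposes a period shift equal to the whole 2 h target; it shows what could go unnoticed and does not forecast that it will. The ranges of 22–65% and 27–39% are illustrative only, since weekly variance and drift are assumed.

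A reader might go further and infer that any benefit the trial shows will be a period artefact. The documents do not support that: they give no evidence that a period shift exists or how large it would be. The finding is that the design cannot tell the two apart.

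**What to change.** 1. In Data analysis, strike the words that equate a period effect with a trend, so that the sentence promises only an examination of trend over time.
2. Keep the week-of-use analysis, labelled as a description of learning or habituation within the second system, and report it with confidence intervals.
3. State that under the single order the paired difference is device plus period, and that no trend result will be used to support or reject the no-period-effect assumption.
4. Reconcile the crossover wording and the sequence test with the Procedures. The sequence test cannot be run unless two orders are used. Even with two orders, a non-significant period contrast from 10 participants without washout would be weak support.
5. Optionally, add a sensitivity comparison of days 1–7 since fitting on each system. It equalises time since fitting but does not remove the confounding with period, and the text should say so.

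A day-level model with a device step and slopes should not be offered as the remedy, because its step is equally confounded.

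Cost: items 1 to 4 are text only, and item 5 uses daily data already to be recorded. The real price is giving up the claim that the period effect was checked.
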